ORI IRB# 00000278

Protocol Version 8/19/2020

Official Title: Talk STEM Familia: Dual-Language Academic Vocabulary-Building Technology to Improve Educational, Career, and Health Outcomes Among Latinx Students

Principal Investigators: [name] and [name].

Oregon Research Behavior Interventions Strategies, dba Influents Innovations

Award No. 2 R44 MD013619-02

Final Version Dated: 5/1/2025

STUDY PROTOCOL

Participant Recruitment, Enrollment, and Overall Design

Families were recruited to participate in the evaluation study via distribution of study information through school districts, community organizations, and community health promoters around the United States. Interested parents who contacted project staff were provided additional information about the study and screened for eligibility; those eligible were consented via phone call or sent online Qualtrics consent form. After signing the consent, primary parents and their participating student completed the pretest/baseline (T1) assessment and then were randomized into the treatment group or waitlist control group. The group assignment lasted 6 months.

Parent/student dyads in the treatment group received the Mi Familia STEM program app and Amazon Alexa with skill programmed onto it. Parent/student dyads in the waitlist control received an Amazon Alexa without the Mi Familia STEM program. Treatment group dyads received reminder text messages to use Mi Familia STEM with their child 3/days a week for approximately 10-minutes. Control group dyads were able to use their Amazon Alexa for normal use. At 3-months, both treatment and waitlist control groups were administered the mid-treatment (T2) questionnaire. Both groups received \$100 for completing the T2 assessment. At 6-months from baseline, both waitlist control and treatment groups received post-treatment (T3) questionnaire. The treatment group also completed a consumer satisfaction and usability questionnaire. After completion of T3 questionnaire, treatment and control dyads received \$100. Following T3, the waitlist control group also received access to the Mi Familia STEM app and Amazon Alexa skill.

Mi Familia STEM Program

The Mi Familia STEM program is a dual-language, vocabulary acquisition learning tool that employs integrated web-app and smart speaker technology (phone app and Amazon Alexa Skill) to engage English learner students, grades 4-8, and their families in evidence-based, culturally relevant, home-based learning activities on 72 scientific academic vocabulary (SAV) words that support success in middle and high-school STEM classes.

Measures

T1, T2, and T3 questionnaires measured student knowledge of academic vocabulary meaning and usage (Academic Vocabulary Meaning (AVM) and Academic Vocabulary Word Usage (AVWU); student SAV usage behaviors and behaviors related to academic learning (Academic Vocabulary Usage Behaviors (AVUB) and Academic Learning Behaviors (ALB); student confidence in using SAV words (Academic Vocabulary Confidence (AVC)); and student interest in choosing STEM careers (STEM).

T1, T2, and T3 questionnaires also measured parent knowledge of SAV meaning and usage (Academic Vocabulary Meaning (AVM) and Academic Vocabulary Word Usage (AVWU); Parent SAV usage behaviors (Academic Vocabulary Usage Behaviors (AVUB)); parent confidence using SAV words (Academic Vocabulary Confidence (AVC)); and parent academic support behaviors (Academic Enabling Behaviors (AEB)).

STATISTICAL ANALYSIS PLAN

The evaluation study had three main goals: (a) determine whether statistically significant condition effects were found between T1 and T3 on the outcome measures; (b) determine the program effect sizes; and (c) determine the parents' and students' reaction to the program and

amount of program use. The evaluation of group effects included an intent-to-treat analysis using mixed-effects growth models with the SAS PROC MIXED software, which was estimated with maximum likelihood. Models included an intercept, defined as the T1 assessment, time coded in months since the T1 assessment, a main effect for condition, and a condition \times time interaction. The condition \times interaction tests whether a change in the outcome from the T1 to T3 assessment significantly differed by condition and is a direct test of the program's efficacy. Cohen's d -statistic is provided as a measure of effect size for the condition \times time effects and follows the convention of .2, .5, and .8 for small, medium, and large, respectively. Examining descriptive statistics for the user satisfaction items provided information on parents' and students' reactions to the program.

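### T1 is taken before randomisation, but the growth model leaves the T1 group difference free and names no covariance structure: the efficacy test is generally less precise than the data allow, and its standard errors cannot be judged

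*Combined protocol and SAP*

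**What the plan says.** The protocol section on recruitment and overall design states that dyads "completed the pretest/baseline (T1) assessment and then were randomized into the treatment group or waitlist control group". The later assessments are T2, at 3 months, and T3, at 6 months from baseline.

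Goal (a) of the Statistical Analysis Plan is to "determine whether statistically significant condition effects were found between T1 and T3 on the outcome measures". The analysis is by intention to treat, "using mixed-effects growth models with the SAS PROC MIXED software, which was estimated with maximum likelihood". On the fixed effects it says: "Models included an intercept, defined as the T1 assessment, time coded in months since the T1 assessment, a main effect for condition", and then adds condition by time. That interaction "tests whether a change in the outcome from the T1 to T3 assessment significantly differed by condition", and the SAP calls it the direct test of efficacy.

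The SAP does not say which random effects are fitted (intercept, or intercept and slope). It gives no residual covariance and no standard-error or degrees-of-freedom method. T1 appears only as a response, not as a covariate.

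**The concern.** With time zero at T1, the condition main effect is the fitted group difference at T1. Randomisation followed T1, so the true T1 means are equal and any observed difference is chance. A model that estimates this difference from the data makes the interaction behave like a comparison of raw change scores. That is usually noisier than an analysis that uses the known equality at T1.

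The missing covariance is a second matter, and it concerns error control. Model-based standard errors from a mixed model are right only if the within-person covariance is adequately modelled. Without knowing what was fitted, a reader cannot tell whether the reported p-values hold their nominal level. Both matters fall on the result that the SAP treats as the main evidence.

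**Working it through.** **Inputs.** From the documents: visits at 0, 3 and 6 months; linear time; free T1 difference. Not in the documents, so assumed: 1:1 allocation, complete data, large sample, two-sided 0.05. Let rho be the T1-T3 correlation and k = SD(T3)/SD(T1), with SD(T1) = 1 and the SD moving linearly to k. The SAP has no power or precision figure to reproduce.

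**Step 1: variances.** Per person, let D = Y3 - Y1 and C = Y1 - 2·Y2 + Y3, and write v and c for variances and covariances. With the covariance correctly specified, the planned estimate (scaled to 6 months) is the group difference in D - b·C, where b = cov(D,C)/var(C).

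- Planned: var(D) - cov(D,C)²/var(C), where var(D) = 1 + k² - 2·rho·k and cov(D,C) = v3 - v1 - 2(c23 - c12).
- Shared T1 mean, visit as a category, unstructured covariance, T3 contrast: k²(1 - rho²). This is the same as T3 adjusted for T1 when data are complete.

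The saving is therefore (1 - rho·k)² - cov(D,C)²/var(C).

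**Step 2: equal SDs (k = 1), compound symmetry.** Here cov(D,C) = 0, so the ratio is (1 - rho²)/[2(1 - rho)] = (1 + rho)/2.

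- rho = 0.5: 0.75/1.00 = 0.75. The planned model would need 1/0.75 = 1.33 times the dyads for equal precision.
- rho = 0.7: 0.51/0.60 = 0.85, and 1/0.85 = 1.18 times the dyads.

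**Step 3: SDs that change.** Worked case, rho = 0.7, k = 1.5, SDs 1, 1.25, 1.5:

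- c12 = 0.875, c13 = 1.05, c23 = 1.3125.
- var(D) = 1 + 2.25 - 2.10 = 1.15.
- cov(D,C) = 2.25 - 1 - 2(0.4375) = 0.375.
- var(C) = 1 + 6.25 + 2.25 - 3.5 + 2.1 - 5.25 = 2.85.
- Planned variance = 1.15 - 0.1406/2.85 = 1.1007; shared T1 = 2.25 × 0.51 = 1.1475; ratio 1.04.

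The same formulas give these ratios (below 1 favours the shared T1 mean):

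| rho | k = 0.8 | 1.0 | 1.2 | 1.3 | 1.5 |
|---|---|---|---|---|---|
| 0.5 | 0.58 | 0.75 | 0.88 | 0.93 | 1.01 |
| 0.7 | 0.64 | 0.85 | 0.98 | 1.01 | 1.04 |
| 0.8 | 0.65 | 0.90 | 1.01 | 1.02 | 0.99 |

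Against a plain change score the gain is (1 - rho·k)² and vanishes at k = 1/rho. Against the planned linear model it vanishes somewhat sooner, because that model also borrows from T2. The 4% loss is the largest in this table but not a ceiling: at rho = 0.5, k = 2 the ratio is 3/(3 - 2.25/7) = 1.12.

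**Step 4: error control of the planned test.** Suppose it was fitted with a random intercept only, and the truth is AR(1) with adjacent correlation a and equal SDs. The true variance of D is 2(1 - a²). The model takes it as 2[1 - (2a + a²)/3]. Type I error is 2Φ(-1.96/√R), where R is true over modelled variance.

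| a | R | type I error |
|---|---|---|
| 0.3 | 0.91/0.77 = 1.18 | 0.071 |
| 0.5 | 0.75/0.583 = 1.29 | 0.084 |
| 0.7 | 0.51/0.37 = 1.38 | 0.095 |
| 0.8 | 0.36/0.253 = 1.42 | 0.100 |

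**Step 5: the shortcut of only deleting the condition term.** Keeping linear time but sharing the T1 intercept moves the estimate away from T3 when the effect is not linear. At rho = 0.5, k = 1:

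- an effect complete by T2 is estimated at 1.09 of its T3 size (planned 1.00);
- one appearing only by T3, at 0.91 (planned 1.00);
- a T2 effect gone by T3 still shows as 0.18 of itself (planned 0.00).

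If that shortcut is taken under a random-intercept-only covariance with SDs growing (rho = 0.7, k = 1.3), type I error is 0.083 against 0.055 for the planned model.

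**The case against.** The planned model is a coherent test of the stated goal. The free condition term also does some useful work: with equal SDs and compound symmetry it absorbs non-linearity, so that the interaction equals T1-to-T3 change whatever happens at T2. That stands. It is why the remedy treats visit as a category rather than deleting a term from the linear-time model. The protection is incomplete, though. At rho = 0.5, k = 1.3 the planned model itself, fitted with the correct covariance, gives 1.09, 0.91 and 0.17 for the three patterns in step 5.

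It is also fair to say that the gain may be nil here. Every ratio rests on assumed values, and positively correlated random intercepts and slopes would push SDs upward and remove most of the benefit. The plan is written in the past tense and marked "Final Version Dated: 5/1/2025", so a change of primary test is probably no longer open. Both points stand, and they limit what can be asked for.

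A reader might infer that a chance T1 imbalance biases the planned test. It does not: with complete data and a linear effect the estimate is unbiased. A reader might instead infer that the issue is only one of efficiency and that the test is otherwise valid. The documents do not support that either, because the covariance on which validity depends is not stated.

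**Conclusion.** The concern holds in a limited form. T1 precedes randomisation, the T1 difference is left free, and T1 is not adjusted for, so the condition by time test is generally less precise than it could be. The loss in this trial cannot be computed. With equal SDs, compound-symmetric correlation, complete data and a correct covariance, the proposed analysis has 0.75 (rho = 0.5) to 0.85 (rho = 0.7) of the planned variance. With growing SDs the advantage goes to zero and can reverse, by up to about 4% for the cases tabulated.

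Validity of the standard errors is undetermined. Type I error of 0.07 to 0.10 is what a random-intercept-only fit would give under the assumed AR(1) correlations. A reader might take it as a finding about this trial, but the SAP names no such fit. With dropout, unbiasedness additionally needs data missing at random and an adequate mean and covariance model. This is worth correcting, with medium confidence in its practical size.

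**What to change.** For each outcome, keep T1, T2 and T3 as responses. Treat visit as a category, give both arms one T1 mean, and allow group differences at T2 and T3 only. Use an unstructured 3×3 within-person covariance and test the T3 difference, with empirical standard errors as a check. Report the effect size for that same contrast. With complete data, adjusting T3 for T1 is an equivalent and simpler route. State the standard-error and degrees-of-freedom method. Whichever model is kept, state the random-effects or covariance structure that was actually fitted for the planned test.

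In PROC MIXED this means a visit CLASS variable, treatment indicators for T2 and T3 in place of condition and its interaction, REPEATED with TYPE=UN, and a second run with EMPIRICAL. There are five fixed effects instead of four, and six covariance parameters. No new data are needed. The statistical price is the small possible loss of precision when SDs grow and the effect really is linear.

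If outcomes have already been analysed, keep the planned test as primary and add this as a labelled sensitivity analysis.

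### The growth model estimates a T1 difference between arms that randomisation makes zero by design, which costs precision on condition × time; adding student grade is a smaller, conditional gain

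*Combined protocol and SAP*

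**What the plan says.** The Statistical Analysis Plan describes an "intent-to-treat analysis using mixed-effects growth models with the SAS PROC MIXED software, which was estimated with maximum likelihood". Its fixed effects are set out in one sentence: "Models included an intercept, defined as the T1 assessment, time coded in months since the T1 assessment, a main effect for condition", followed by condition × time. The interaction "tests whether a change in the outcome from the T1 to T3 assessment significantly differed by condition" and is named as the direct test of efficacy. No baseline covariate is listed.

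The section on recruitment, enrollment and overall design fixes the order of events. Dyads "completed the pretest/baseline (T1) assessment and then were randomized into the treatment group or waitlist control group". Follow-up is at 3 months ("At 3-months, both treatment and waitlist control groups were administered the mid-treatment (T2) questionnaire") and at 6 months (T3).

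On grade, the Mi Familia STEM Program section says the tool is meant "to engage English learner students, grades 4-8, and their families". The recruitment text says that interested parents "were provided additional information about the study and screened for eligibility", without listing criteria or recorded variables.

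**The concern.** Because time is zero at T1, the condition main effect is the T1 difference between arms. T1 comes before randomisation, so any T1 difference is chance. Giving each arm its own T1 mean discards that knowledge. The interaction then compares changes from two separately estimated starting points, and the noise in both passes into the efficacy contrast. A shared T1 mean removes it with no new data.

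The students may also span five school grades, and grade plausibly predicts science vocabulary. That invites the thought that adjusting for grade would sharpen the test. Whether it does depends on how T1 is handled, so the two matters have to be taken together.

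At stake is the width of the interval for the plan's main effect on every outcome, and the Cohen's d derived from it.

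**Working it through.** **No figure to reproduce.** The documents give no sample size, alpha, power, standard deviation, correlation or dropout rate. What follows compares standard errors under stated assumptions.

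**Inputs from the documents.** Assessments at t = 0, 3, 6 months; linear time in months; a mixed-effects growth model; randomisation after T1.

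**Assumptions.** 1:1 allocation; complete data; T1 variance scaled to 1; between-child share s = 0.5 to 0.8, residual variance 1 − s; random-slope variance 0 or 0.005 per month squared; grade–T1 correlation r = 0.2 to 0.4; grade explaining 0% or 10% of slope variance.

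**Step 1: formulas.** Let V be the 3 × 3 covariance of one child's scores, **1** a column of ones and t = (0, 3, 6). Put A = t′V⁻¹t, B = **1**′V⁻¹t, C = **1**′V⁻¹**1**. With N dyads:
- Planned model (condition and condition × time): Var = 4 / [N(A − B²/C)]
- Common T1 mean (condition × time only): Var = 4 / (N A)
- SE ratio, common to planned: √(1 − B²/(AC)). N cancels.

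**Step 2: numbers.**

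| Share s | Slope variance | Intercept–slope covariance | A | B | C | B²/(AC) | SE ratio | SE reduction |
|---|---|---|---|---|---|---|---|---|
| 0.5 | 0 | 0 | 49.500 | 4.500 | 1.500 | 0.2727 | 0.8528 | 14.7% |
| 0.8 | 0 | 0 | 100.385 | 3.462 | 1.154 | 0.1034 | 0.9469 | 5.3% |
| 0.5 | 0.005 | 0 | 39.679 | 3.607 | 1.419 | 0.2311 | 0.8769 | 12.3% |
| 0.8 | 0.005 | 0 | 66.837 | 2.305 | 1.114 | 0.0713 | 0.9637 | 3.6% |
| 0.8 | 0.005 | 0.0089 | 64.534 | 1.628 | 1.076 | 0.0382 | 0.9807 | 1.9% |

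The last row lets grade drive both level and slope, which induces a covariance of 0.4 × √(0.1 × 0.005) = 0.0089. The range is therefore about 2% to 15%. As a multiple of sample size this is 1/0.9807² = 1.04 to 1/0.8528² = 1.375, or about 4% to 38% more dyads. For a comparison with 80% power at two-sided 5%, power becomes Φ(2.802/0.9807 − 1.960) = 0.815 to Φ(2.802/0.8528 − 1.960) = 0.907.

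**Step 3: grade in the planned model.** With a random intercept only, A − B²/C = 18/(1 − s). Between-child variance does not appear, so a covariate that explains level alone cannot help. Forty simulated datasets (N = 200, grade explaining half the intercept variance) agree: the condition × time estimate was the same with and without a grade main effect, and its mean standard error was 0.02111 both ways. With 20% dropout the SE ratio was 0.997 to 1.000. Adding grade × time as well gives a 0% reduction if grade does not predict slope, and 0.8% to 1.6% if it explains 10% of slope variance.

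**Step 4: grade with a common T1 mean.** Grade now removes variance that a single imperfect T1 score leaves behind. Take s = 0.5, no random slope and r = 0.4. Intercept variance falls to 0.5 − 0.16 = 0.34, and A rises to (45 − 81 × 0.34/1.52)/0.5 = 53.76. The SE ratio is √(49.50/53.76) = 0.960, a further 4% reduction. Across the assumed range the further reduction is 0.2% to 4% if grade does not predict slope, and about 3% to 7% if it explains 10% of slope variance and higher grades both start higher and gain faster. Both changes together give about 4% to 18%.

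**The case against.** The planned model is conventional and valid. Randomisation protects the comparison, a chance T1 difference is already reflected in the standard error, and nothing in the documents contradicts the chosen terms. All of that stands, so the point concerns efficiency only.

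The gain also depends on variances the documents do not give. It shrinks when children who start higher also gain faster. With s = 0.8, slope variance 0.005 and an intercept–slope correlation of 0.3, the covariance is 0.3 × √(0.8 × 0.005) = 0.0190, B²/(AC) = 0.934²/(62.902 × 1.048) = 0.0132, and the reduction is only 0.7%.

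A common T1 mean leans harder on linear time. Suppose the whole effect d appears by 3 months and then holds. With s = 0.5 and no random slope, the planned model gives 6 × d/6 = d at T3, and the constrained model gives 6 × 9d/49.5 = 1.09d. This deserves a check; it does not defeat the change.

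A reader might infer that leaving out grade is the main loss, or that it biases the result. Neither is supported. In the planned model the grade terms cut the standard error by at most 1.6% under these assumptions, and they cost slightly (ratio up to 1.009) in small samples if grade does not predict change. Chance grade imbalance is sampling error. Nor do the documents say that grade was recorded: grades 4–8 describes the program's audience, and the content of screening is not given.

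Finally, the plan is dated 5/1/2025 and written in the past tense, so a change of model now may be post hoc.

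**Conclusion.** The point holds as a modest, nearly free gain in precision. The T1 condition term estimates a quantity that is zero by design, and removing it lowers the standard error of condition × time by about 2% to 15% under the Step 2 assumptions, or less if intercept and slope are more strongly positively correlated. Grade is secondary. Its further gain of 0.2% to 7% depends on the common baseline, on grade having been recorded and, for the upper part, on grade predicting slope, for which the documents offer no evidence. The conclusion also rests on a child-level random effect, which the description as a mixed-effects growth model implies but does not spell out.

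**What to change.** - In PROC MIXED, drop the condition main effect so that both arms share one T1 mean; keep time and condition × time, and report the condition effect at T3 from that model. This applies to student and parent outcomes alike.
- State the random-effects structure. As a check on linearity, refit with time as a category and the T1 means still equal.
- Ask the sponsor whether student grade was recorded at baseline. If so, add grade (linear, 4–8) and grade × time to the six student-outcome models. Parent models need no grade term.
- If outcomes have already been analysed, keep the planned model as primary and report this one as a labelled sensitivity analysis.

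Cost: a sentence or two in the plan and one fewer model term, plus two degrees of freedom if grade is used. No new data are needed, provided grade is on file.

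### The condition × time slope equals the T1-to-T3 effect only if T3 is complete or change is linear, and the SAP does not say so

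*Combined protocol and SAP*

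**What the plan says.** Goal (a) of the Statistical Analysis Plan is to "determine whether statistically significant condition effects were found between T1 and T3 on the outcome measures". The evaluation of group effects "included an intent-to-treat analysis using mixed-effects growth models", fitted by maximum likelihood in SAS PROC MIXED. The fixed terms listed are the intercept at T1, "time coded in months since the T1 assessment", condition, and condition × time. There is no quadratic, piecewise or visit-class term. The SAP then states that the interaction "tests whether a change in the outcome from the T1 to T3 assessment significantly differed by condition" and presents it as the direct efficacy test. Cohen's d "is provided as a measure of effect size for the condition" × time effects, so it rests on the same coefficient.

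The section on recruitment, enrollment and overall design fixes the visit times: "At 3-months, both treatment and waitlist control groups were administered the mid-treatment (T2) questionnaire", and "At 6-months from baseline, both waitlist control and treatment groups received post-treatment (T3) questionnaire".

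The documents give no covariance structure, rule for missing assessments, expected T3 loss or check of linearity. The word linear does not appear. The straight-line reading follows from a single time term in months in a growth model.

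**The concern.** A slope and an endpoint change are different quantities. With three visits they coincide only under conditions the SAP does not state. A maximum-likelihood fit on the intent-to-treat set keeps dyads that have T1 and T2 but no T3. Under a straight-line mean, those dyads inform the slope through their 0-to-3-month change, which is in effect projected to month 6. If the true course bends, that projection is wrong.

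The term named as the efficacy test could then be biased for the T1-to-T3 effect: upward if gains come early and level off, downward if they come late. It could be non-zero when the T1-to-T3 effect is zero, either because an effect at T2 has faded by T3 or because both arms share one curved course and lose different shares of T3. The plan applies the same model to every student and parent outcome, and these need not share one trajectory.

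**Working it through.** The plan states no figure to reproduce. The check is of its verbal claim that the interaction equals the T1-to-T3 comparison.

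**Inputs.** From the documents: visits at months 0, 3 and 6; linear time; maximum likelihood. Assumed, because the documents are silent: T1 SD = 1; random intercept with within-person correlation ρ = 0.5–0.7; T3 loss of 5–40%, unrelated to outcome and equal by arm unless stated; visits at nominal times; control arm flat unless stated. The 0.5 SD used for illustration is the SAP's medium effect.

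**Step 1: complete data.** Centred times are −3, 0, 3, so slope = (3·T3 − 3·T1)/18 and 6 × slope = T3 − T1. The weights on (T1, T2, T3) are (−1, 0, 1). Generalised least squares gives the same under random-intercept, random-slope and AR(1) covariances, and also when only T2 is missing (20%, random intercept, ρ = 0.6). The SAP sentence is correct here.

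**Step 2: some T3 missing.** The weights must sum to zero and must be exact for a straight line. That leaves one free number, L:

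6 × slope = (1 − L)(T3 − T1) + L × 2(T2 − T1)

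Write D2 and D3 for the between-arm differences in change from T1 to T2 and from T1 to T3. With equal loss in both arms,

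bias = L × (2·D2 − D3),

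which is zero when the course is linear (D3 = 2·D2).

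**Step 3: L at ρ = 0.6 and 20% loss.** Use 3-month units, k₃ = ρ/(1 + 2ρ) = 0.6/2.2 = 0.2727 and k₂ = ρ/(1 + ρ) = 0.6/1.6 = 0.375. Up to a common factor, the information matrices are:

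- all three visits: [[3 − 9k₃, 3 − 9k₃], [3 − 9k₃, 5 − 9k₃]] = [[0.545, 0.545], [0.545, 2.545]]
- T1 and T2 only: [[2 − 4k₂, 1 − 2k₂], [1 − 2k₂, 1 − k₂]] = [[0.5, 0.25], [0.25, 0.625]]

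Mixed 0.8 to 0.2, they give [[0.5364, 0.4864], [0.4864, 2.1614]], determinant 0.923. The T3 score is 0.8 × (1 − 3k₃, 2 − 3k₃) = (0.1455, 0.9455). The slope's weight on T3 is (0.5364 × 0.9455 − 0.4864 × 0.1455)/0.923 = 0.473. Over two units this is 0.946, so L = 0.054 and the weights are (−1.054, 0.108, 0.946).

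**Step 4: expected value of 6 × (condition × time), ρ from 0.5 to 0.7.**

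| Course (T2, T3 effect in SD) | True T3 effect | 10% loss | 20% loss | 40% loss |
|---|---|---|---|---|
| Linear (0.25, 0.5) | 0.500 | 0.500 | 0.500 | 0.500 |
| Plateau (0.5, 0.5) | 0.500 | 0.512–0.513 | 0.526–0.528 | 0.565–0.568 |
| Late (0.1, 0.5) | 0.500 | 0.493–0.492 | 0.484–0.483 | 0.461–0.459 |
| Fully late (0, 0.5) | 0.500 | – | 0.474–0.472 | 0.436–0.432 |
| T2 only (0.5, 0) | 0 | 0.024–0.026 | 0.053–0.056 | 0.129–0.136 |

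At 5% loss the plateau gives 0.506. As a check on the formula at ρ = 0.6 and 20% loss, plateau bias = 0.054 × (2 × 0.5 − 0.5) = 0.027.

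**Step 5: no program effect, unequal loss.** Both arms rise 0.5 SD by T2 and then level off; T3 loss is 30% in treatment and 10% in control. At ρ = 0.6, L = 0.0894 and 0.0248, so the spurious difference is (0.0894 − 0.0248) × 0.5 = 0.032 SD (0.031–0.033 over ρ = 0.5–0.7). A late-rising shared curve reverses the sign, as does swapping which arm loses more. Equal loss gives 0.

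**Step 6: other covariances.** With random slopes or AR(1), L is larger. Over all structures tried, including random intercepts with ρ from 0.4 to 0.8, the plateau gives 0.525–0.549 at 20% loss and 0.563–0.613 at 40%.

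**Step 7: simulation.** With 8,000 per arm, ρ = 0.6 and 20% loss, the maximum-likelihood linear estimate minus the visit-based estimate was +0.025 (plateau), +0.057 (T2 only) and −0.017 (late), against +0.027, +0.054 and −0.016 from the formula.

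**The case against.** The best defence is that the sentence can be read as change over the T1–T3 period. In a growth model the interaction is then a difference in rate, and no mismatch arises. This does not hold. The average rate over the period is still (T3 − T1)/6, and the fitted slope departs from it by an amount set by who is missing at T3.

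Three other points stand, within limits.

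- **Both conditions are needed, and neither is documented.** The fault requires T3 loss and curvature together. The T3 payment and the waitlist arm's access after T3 may help retention, though they do not establish it.
- **The size is modest at ordinary loss.** At 10–20% loss a complete plateau moves a d of 0.5 by 0.012–0.028 under a random intercept. In the unequal-loss null case, with an assumed 50–200 per arm, the nominal two-sided 5% error rate becomes 5.2–6.8%; the excess grows with sample size.
- **The analysis may already be done.** The SAP is written in the past tense, so changing the efficacy contrast could be post hoc. That calls for open labelling. It does not make the stated interpretation correct.

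**Conclusion.** The concern holds, as a conditional one. The SAP's reading of the interaction is exact with complete T3 data under the covariances tried, and exact for a linear course at any loss. It fails when T3 is missing for some dyads and the course is curved, and the SAP does not state that dependence.

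Under a random intercept with T3 loss unrelated to outcome, the error for a plateau or fully late gain of 0.5 SD is 5–6% of the effect at 20% loss and 13–14% at 40%, upward for the first and downward for the second. Random slopes make it larger. The more serious cases are those where the T1-to-T3 effect is zero and the term is not: 0.05–0.06 SD for a faded T2 effect at 20% loss, and about 0.03 SD for a shared curve with 30% against 10% loss. Loss, covariance and trajectory are all assumptions, so bias in this trial is possible, not shown. The change is worth making because it costs little and matches goal (a).

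**What to change.** In the same mixed model, enter time as a three-level class variable (T1, T2, T3) with condition × visit. Define efficacy as the condition difference in T3-minus-T1 change and compute Cohen's d from that contrast. Its weights are (−1, 0, 1), so under the assumptions above it returns the true T3 effect for every course in the table.

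Keep the linear slope as a sensitivity analysis and state that its T1-to-T3 reading assumes linear change when T3 is missing. Report by arm how many dyads have T2 but no T3. If results have already been seen, report both analyses and say which was added.

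The cost is one CLASS variable and one contrast on data already collected. With complete data under random-intercept or standard random-slope covariance, estimate and precision are unchanged. If T3 is missing and growth really is linear, the standard error rises by about 0.1% at 10% loss, 0.4% at 20% and 2% at 40% (random intercept).

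### Does leaving the formula for Cohen's d unstated undermine the effect-size goal?

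*Combined protocol and SAP*

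**What the plan says.** The Statistical Analysis Plan lists three goals, the second being to "determine the program effect sizes". For that goal it says: "Cohen's d -statistic is provided as a measure of effect size for the condition" by time effects, and that the statistic "follows the convention of .2, .5, and .8 for small, medium, and large, respectively".

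The effect being standardised comes from a mixed-effects growth model fitted by maximum likelihood, with "time coded in months since the T1 assessment". The interaction is described as a test of whether change "from the T1 to T3 assessment significantly differed by condition". Under Participant Recruitment, Enrollment, and Overall Design, T2 falls at 3 months and T3 at 6 months.

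The document does not give a formula for d, a named standard deviation, a statement that the monthly coefficient is multiplied by six, or a rule for deriving d from a t statistic.

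**The concern.** In its textbook form, Cohen's d is a difference between two group means over a pooled raw-score SD. Here it is attached to an interaction coefficient from a repeated-measures model, where several denominators are in use: the baseline SD, the SD of change scores and the model's residual SD. Some analysts instead convert the t statistic, and that result depends on the degrees of freedom. Because time is in months, the raw coefficient is also a per-month quantity.

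These versions can differ by more than a label's width. If they do, a reader cannot reproduce d from the plan alone or know what small, medium or large refers to. There are 11 outcomes under Measures (six student, five parent). A change-score or residual d would rank them partly by how stable each measure is over six months and not only by how far the program moved it.

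**Working it through.** **What can be reproduced.** The document gives no d, SD, correlation or sample size, so there is no figure of the plan's own to recompute. The check is how far the label depends on the choice of denominator.

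**Inputs.** From the document: follow-up of 6 months and cut-offs of .2, .5 and .8. Assumed: T1 SD = 1, equal SD at T3, six-month difference in change D = 0.40, and T1–T3 correlation r from 0 to 0.9.

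**Formulas.**
- Baseline SD: d = D / 1.
- Change-score SD: d = D / √(2(1 − r)).
- Residual SD: d = D / √(1 − r). This holds only for a random-intercept model with r equal to the intraclass correlation. The plan does not name its random effects, so this row is conditional.

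| Denominator | r = 0 | 0.3 | 0.5 | 0.7 | 0.8 | 0.9 |
|---|---|---|---|---|---|---|
| Baseline SD | 0.40 | 0.40 | 0.40 | 0.40 | 0.40 | 0.40 |
| Change-score SD | 0.28 | 0.34 | 0.40 | 0.52 | 0.63 | 0.89 |
| Residual SD (conditional) | 0.40 | 0.48 | 0.57 | 0.73 | 0.89 | 1.26 |

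**Where labels part.**
- Residual-SD d reaches .5 when √(1 − r) = 0.40/0.50 = 0.8, so r = 1 − 0.64 = 0.36. It reaches .8 when √(1 − r) = 0.5, so r = 0.75.
- Change-score d reaches .5 when 2(1 − r) = 0.64, so r = 0.68. It reaches .8 when 2(1 − r) = 0.25, so r = 0.875.
- All three therefore say small below r = 0.36, and the baseline and change-score versions share that label up to r = 0.68.

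**Unscaled monthly coefficient.** 0.40/6 = 0.067, which is below small. This reading does not fit the plan, which describes the interaction as a difference in change from T1 to T3. The numerator is therefore reasonably settled as six times the monthly coefficient.

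**d from t.** Take r = 0.7, 100 dyads per arm (assumed), visits at 0, 3 and 6 months (sum of squared deviations 9 + 0 + 9 = 18) and a random-intercept model.
- SE = √(2 × 0.3 / (100 × 18)) = 0.01826, and t = 0.0667/0.01826 = 3.65.
- 2t/√df = 7.30/√198 = 0.52 with subject-level df, or 7.30/√398 = 0.37 with within-subject df.

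This is a further legitimate variant, with the same modest spread.

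**What depends on d.** The efficacy test is the interaction test. Its estimate, standard error and p-value are the same whichever denominator is later used. The plan states no sample size, success criterion or stopping rule tied to d or its label.

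**The case for a change.** The strongest case for a change is that effect size is one of only three goals, the sentence on d is complete and not redacted, and the label can run from small to large for one and the same effect. A single added sentence would settle it without new data or models. The arithmetic behind this stands, and so does the statement that d cannot be reproduced from the plan alone.

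Several parts carry less weight than they seem to.
- Every magnitude rests on an assumed effect and correlation, and the widest gaps also need a random-intercept model that the plan does not specify.
- Asking only for a named denominator would not make the 11 outcomes comparable. A change-score or residual d varies with r whether or not it is named; only a raw-score SD avoids this, and the plan already allows it.
- Nothing can be inferred about when the standardiser was chosen. The header carries a protocol version of 8/19/2020 as well as "Final Version Dated: 5/1/2025", and neither date shows when this sentence was written.

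**Conclusion.** No change is called for. The omission is real, but it is missing detail in a short plan and not a rule that yields a wrong result. The plan names the effect, points to the six-month interval and fixes the cut-offs. An analyst who follows the usual meaning of Cohen's d would divide the six-month difference by a raw-score SD and obtain 0.40 in the example at every correlation. That choice is correct and fully consistent with the text.

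The possible discrepancy is confined to a descriptive label: none below r = 0.36, and up to two categories at r = 0.8, given D = 0.40, equal SDs at T1 and T3 and, for the residual version, a random-intercept model. The efficacy test is untouched. The natural place for the formula is beside the reported values of d. The document does not show that it will be left out there, or that any d has been miscalculated.
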